## B.7 Rationale for Cross-Population or “Ecological” Studies

We have now missed the historical moment when obesity risk factors changed in the US. By sampling from global populations across the range from low to high risk, we can compress the time dimension and model this transition with standard epidemiologic methods. In the past, this “population as the unit of analysis” design has made crucial contributions to research in common disease. The key role of nutrition as the underlying cause of the CHD epidemic was first recognized by ecological comparisons [75]. The “Seven Countries Study” subsequently demonstrated the relationship of individual nutrients to atherosclerosis [75-78]. “Intersalt” employed a similar design to study mineral intake and blood pressure [79, 80], and our recently completed “International Collaborative Study on Hypertension in Blacks” (ICSHIB) used population comparisons to examine a broad range of risk factors and physiologic processes in hypertension (cf C.2.3) [81]. Similar studies have suggested etiologic factors for breast, colon and stomach cancer. The study proposed here will extend this methodology into the area of obesity for the first time. The advantages and disadvantages of this design are outlined in general terms in the section below and in more detail under Methods (Section D).

Descriptive epidemiology is usually the only available tool that can be used to examine etiologic processes in chronic disease. For many “common source” diseases, however, methodological problems undermine its effectiveness. Within a homogeneous society some degree of exposure may be universal, and the relevant quantitative variation can be hard to characterize. This is often complicated by large *within-person* relative to *between-person* variation in the exposures which makes person-level analyses imprecise. The large contrasts obtained by comparing social groups as the unit of analysis and the marked shifts that occur among migrants can help focus attention on the key exposures. For example, in ICSHIB low correlations were noted between BMI and Na with BP at the individual level (.01-.15); however, these rose to 0.85 when populations were the unit of analysis. As with all study designs, however, there are trade-offs in cross-cultural studies. For example, a concern sometimes raised is the “ecologic fallacy,” whereby group-level relationships are falsely inferred to be causal at the individual level [82]. We are well aware of this potential threat and address it further in the analytic section of the Methods. With consistency at both levels and control for confounding, however, these relationships can be inferred with confidence. Likewise, once a strong hypothesis has been established, larger within-population studies can be justified.

## B.8 Adipocytokines, Appetite Hormones and Regulation of Body Fat Stores.

Once considered metabolically inert, adipose tissue has now been shown to secrete multiple cytokine hormones [83-85]. In addition, other components of the system that regulates body fat stores have been identified [21, 86]. Despite initial enthusiasm, from this long list—which includes, among others, leptin, adiponectin, ghrelin, resistin, visfatin, omentin, NPY3, serum amyloid A, TNF- $\alpha$ , RBP4, IL-6, IL-10—only for the first 3 is there reasonable evidence of a physiologic function in regulating fat mass or influencing EE [22, 87, 88]. Leptin accurately reflects fat mass, and, while not an “adipostat”, appears to function at the lower range to prevent depletion of calorie reserves [89]. Adiponectin is a potent insulin sensitizing agent, and in prospective studies—including our own—it predicts onset of glucose intolerance [90, 91]. Surprisingly, adiponectin is not higher in women than men despite higher body fat, and it varies cross-culturally with BMI [92], suggesting a more complex role that has not yet been defined. Ghrelin, which is secreted by the stomach, clearly

contributes to appetite control but is more complex to study in observational cohorts [93, 94]. Although data in the literature are inconsistent as to whether or not these hormones, in concert with insulin, play a role in the regulation of energy balance [95-103], four recent studies suggest associations with EE independent of body composition for all three, adiponectin, leptin and ghrelin [104-107], and we will measure them in all subjects. Additional inter-relations to EE from our pilot data are described in section C below.

## B.9 Summary

Although the “obesity epidemic” has received enormous attention in recent years, the mechanisms through which the energy budget is being perturbed are still not well understood. In particular, the role of declining AEE as a causal mechanism in population-wide increases in relative weight deserves much greater attention. Despite widespread perception that variation in normal activity levels (as opposed to voluntary increases in high-intensity activity, as typical of trials) is correlated with change in weight, the data do not support this conclusion. Research in this vital area has been handicapped by lack of access to precise objective methods of measurement. A new generation of epidemiologic research will be required before we can base causal inferences or public health recommendations on something more than assumptions. As with other chronic CVD, international comparisons could be particularly informative.

The test of our study hypothesis will be “two-sided”. That is to say, the presence or absence of an association can be given a clear interpretation. Of course, given the body of evidence that increased AEE has health advantages, absence of an association would not be taken to suggest that AEE is of no value. Rather, the correct interpretation would be that declining AEE is unlikely to be the driving force behind the rise in obesity, nor will modest increases in AEE be adequate to reverse the trends.

## C. PRELIMINARY STUDIES

### C.1 Experience in International Collaborative Research

#### C.1.1 Experience of the PI

The applicant is a nutrition epidemiologist with a primary interest in AEE and obesity. Her doctoral thesis involved the development of improved laboratory methods for the analysis of stable isotopes to measure AEE [108-111]. At Loyola she has been involved in large-scale cross-cultural studies comparing CV risk status, nutrition and AEE in populations of African descent in Nigeria, Jamaica and Chicago [112-120]. She is currently PI on a grant to define AEE and obesity risk in women in rural Nigeria and Chicago; the preliminary data from Nigeria-Chicago comparisons provide part of the framework for this study. This project represents the largest cross-cultural application of DLW to population samples. As part of a related project, she has collected resting EE data on 2,500 individuals in Nigeria, Jamaica, and the US—the largest such sample ever studied [114, 121].

In Chicago she has supervised studies enrolling more than 2,000 African-American and Mexican-American participants over the last 6 years. She recruited and supervised bilingual staff and established effective working relationships with communities and local institutions. The PI is also working as a consultant with the Tropical Medicine Research Institute of the University of the West Indies in Kingston, Jamaica, on an International Atomic Energy Agency-sponsored project [118]. The project is designed to assess EE and intake in both rural and urban older adults using the DLW method and their relationship to parameters of glucose tolerance in populations at elevated risk of diabetes.

#### C.1.2 Experience within the Department

[figure not shown]
The applicants have extensive experience in collaborative research. In 1992, the Department initiated the largest international study of hypertension yet to be conducted, involving 12,000 participants in 8 countries of African origin [112, 122-124]. This research project has produced comparable population prevalence estimates, new insights into physiologic pathways, estimates of disease burden from prospective cohorts, and numerous genetic analyses [125-128]. The study has been continuously funded by the NIH for 15 years. The PI has participated actively in all aspects of this collaborative program and has extensive field experience in

Africa and the Caribbean. The Department of Preventive Medicine has additional collaborative research in Mexico, Cuba and Puerto Rico.

## C.2 Previous Research on Physical Activity, DLW, Body Composition and Weight Change

### C.2.1 Physical Activity by Accelerometer

**Figure 4**

Accelerometers have been used by the applicants to measure AEE in all of the study sites; in addition, our consultants, Drs. [name] and [name], have published extensively on the methodology and validation of accelerometry [129-134]. In preparation for this application, preliminary data have been collected in all 5 populations using the proposed AEE protocol (Table 1). In each of the field sites, men and women were recruited and wore the accelerometer (Actical, Respiration/Mini-Mitter, Bend, OR) for a minimum of 7 consecutive days.

Our experience with the accelerometers was overwhelmingly positive at each of the sites. Acceptance of the instruments by the participants was uniformly high, there were no instances of instrument failure with accompanying loss of data, no reports of excessive participant burden, and virtually no missing data due to non-compliance by participants (cf. D4.1.1 for further details).

Over the course of 3 months we enrolled 198 adults. As can be observed in Table 1, there is a range of mean activity EE measured by the accelerometers across the sites with the highest levels recorded among Jamaican and South African males and the lowest among women from Nigeria and the Seychelles.

**Table 1. Participant Characteristics by Site – mean (SD)**

	Jamaica	Maywood	Nigeria	Seychelles	S. Africa
n (M/F)	41 (18/23)	36 (16/20)	38 (20/18)	45 (22/23)	38 (16/22)
Age (yrs)	37.9 (8.6)	38.3 ± 10.1	38.9 ± 13.2	35.2 ± 5.7	27.2 ± 5.0
BMI					
males	23.6 (3.5)	27.3 ± 6.5	22.5 ± 2.9	26.6 ± 3.3	21.8 ± 2.0
females	30.6 (5.3)	33.7 ± 9.4	26.2 ± 6.4	26.9 ± 6.4	29.8 ± 7.3
Activity Counts					
males (cts/d)	364040 (158584)	313988 ± 217868	241191 ± 103401	275078 ± 130813	379480 ± 159859
females	209277 (94637)	280929 ± 175078	181312 ± 105667	170670 ± 76242	293548 ± 182584
AEE (kcal/d)					
males	1050 (306)	1090 ± 387	688 ± 253	902 ± 254	911 ± 329
females	884 (306)	1090 ± 566	608 ± 230	617 ± 292	1000 ± 514
AEE/kg (kcal/kg/d)					
males	15.06 (3.76)	13.25 ± 5.71	10.45 ± 3.83	11.45 ± 3.08	14.37 ± 5.35
females	11.13 (3.75)	12.42 ± 5.66	9.14 ± 3.88	8.73 ± 3.16	13.29 ± 6.06
AEE adj. for wt					
males (kcal/d)	1094 (271)	985 ± 426	761 ± 262	866 ± 239	1011 ± 319
females	838 (287)	970 ± 532	660 ± 220	667 ± 227	999 ± 467
Pop. Mean BMI*					
males	23.7 (4.5)	26.7 (5.5)	22.6 (4.5)	25.1 (4.4)	22.9 (6.0)
females	28.0 (6.4)	29.8 (8.1)	22.9 (6.0)	27.6 (6.3)	27.1 (9.1)

\* Population mean BMI for 25-45 year olds based on representative sampling

The absolute activity EE levels are supported by data on the % of time spent in sedentary vs. moderate activity, with Jamaican and South African males, who were primarily laborers, spending less time in sedentary activity than Nigerian or Seychelles women, as recorded by the accelerometer (Table 2). There was an inverse association between activity counts and BMI (Figure 4) indicating a cross-sectional relationship between adiposity and PA. We acknowledge that heterogeneity exists by gender, but caution against interpretation of sub-groups given the small sample size.

Due to varying degrees of literacy amongst our populations, we did not require participants to record activity in a log while wearing the accelerometer. We did, however, have participants in Nigeria and the Seychelles complete the Global Physical Activity Questionnaire (GPAQ) via interviewer. The purpose of the GPAQ is to obtain internationally comparable data on self-reported, health-related AEE done in the past 7 days. The correlation for activity EE (kcal/d) between the GPAQ and the accelerometer,  $r = 0.51$  ( $p < 0.002$ ), did not differ significantly between Nigeria and Seychelles. In both sites the GPAQ overestimated AEE by as much as 145 kcal/d. The GPAQ or other comparable questionnaire used in conjunction with accelerometry can provide useful information on types and patterns of PA.

**Table 2. Average Percent of Awake Time Spent in Varying Levels of Physical Activity by Site**

	Jamaica	Maywood	Nigeria (Mean $\pm$ SD)	Seychelles	S. Africa
Sedentary Activity (%)	$43.3 \pm 11.3$	$46.6 \pm 15.6$	$57.7 \pm 13.6$	$53.0 \pm 11.3$	$40.9 \pm 20.7$
males	$39.7 \pm 8.9$	$46.3 \pm 14.4$	$56.8 \pm 14.4$	$49.6 \pm 9.5$	$41.5 \pm 18.4$
females	$46.0 \pm 12.4$	$46.8 \pm 16.8$	$58.7 \pm 13.1$	$56.3 \pm 12.1$	$40.4 \pm 22.7$
Light Activity (%)	$31.9 \pm 7.4$	$27.9 \pm 6.1$	$22.3 \pm 6.3$	$28.8 \pm 6.0$	$33.6 \pm 11.2$
males	$30.3 \pm 8.9$	$27.7 \pm 5.6$	$21.7 \pm 7.2$	$29.9 \pm 5.7$	$32.2 \pm 9.5$
females	$33.1 \pm 5.8$	$28.0 \pm 6.6$	$23.0 \pm 5.4$	$27.7 \pm 6.2$	$34.5 \pm 12.4$
Moderate Activity (%)	$24.7 \pm 9.9$	$25.2 \pm 12.7$	$19.9 \pm 8.4$	$17.9 \pm 6.2$	$25.1 \pm 11.5$
males	$29.6 \pm 9.0$	$25.5 \pm 11.9$	$21.4 \pm 8.4$	$20.0 \pm 4.8$	$25.4 \pm 11.9$
females	$20.9 \pm 9.0$	$24.9 \pm 13.5$	$18.3 \pm 8.4$	$15.9 \pm 6.7$	$24.9 \pm 11.5$
Vigorous Activity (%)	$0.13 \pm 0.42$	$0.40 \pm 0.78$	$0.05 \pm 0.13$	$0.30 \pm 0.65$	$0.47 \pm 0.82$
males	$0.28 \pm 0.60$	$0.58 \pm 1.09$	$0.08 \pm 0.18$	$0.52 \pm 0.85$	$0.84 \pm 0.90$
females	$0.01 \pm 0.04$	$0.25 \pm 0.37$	$0.01 \pm 0.02$	$0.09 \pm 0.23$	$0.20 \pm 0.65$

## C.2.2 Doubly Labeled Water Studies

### C.2.2.1 DLW & Accelerometer in South Africa

In South Africa, DLW was used to assess free-living total daily EE in a small sample of adults ( $n = 27$ ). Of this total, 18 also wore the Actical accelerometer.

The characteristics of the participants wearing the accelerometer and undergoing DLW did not differ from those listed in Table 1 for South Africa. The total daily EE measured using DLW was  $2600 \pm 655$  kcal/d and using the accelerometer was  $2775 \pm 990$  kcal/d; the correlation was  $r=0.6$ . This pilot study was conducted in Khayelitsha, the community in which we propose to carry out this larger study. The correlation between total EE measured using DLW and the accelerometer was comparable to our weighted correlation calculated from published literature (Appendix A, Table 2), giving us confidence that the accelerometer is measuring the same domain in the field setting that it is in more tightly controlled laboratory settings.

**Table 3. Participant Characteristics – Loyola-Ibadan Women’s Study - mean (SD)**

	Nigeria (n = 150)	US (n = 180)
Age (y)	32.9 (11.4)	33.9 (10.8)
Weight (kg)	58.1 (12.5)	83.6 (21.6)
BMI	23.0 (5.1)	30.9 (7.7)
Fat-free mass (kg)	40.4 (5.3)	48.9 (8.6)
Fat mass (kg)	17.9 (8.8)	34.8 (15.4)
% Body Fat	29.3 (8.6)	39.8 (9.0)
Total EE (kcal/d)	2262 (398)	2442 (462)
Resting EE (kcal/d)	1284 (157)	1400 (212)
PAL (TEE/REE)	1.77 (0.27)	1.75 (0.24)
AEE/kg (kcal/kg/d)	13.5 (6.0) *	10.0 (3.8)
Adj. AEE (kcal/d)	810 (311)	765 (299)

\*  $p < 0.05$

### C.2.2.2 Physical Activity and Weight Change

[figure not shown]
The Loyola-Ibadan Women's Study was initiated in 2000 to study the relationship between resting EE, AEE, and weight change in women from two contrasting social settings. In both metropolitan Chicago and rural Nigeria, women were enrolled in a longitudinal survey in which EE was measured at baseline using DLW, and weight and body composition were measured for 3 consecutive years (Table 3) [135]. Mean change in weight during the follow-up interval was 0.73 and 0.76 kg/y for the Nigerian and US women, respectively. Contrary to our hypothesis, no association was observed between activity EE at baseline and weight change in either site [136]. This result underscores our prior assertion that variation in AEE in free-living populations has not been convincingly shown to predict risk of obesity. Unfortunately, the sample size in this cohort is somewhat small, and we were limited to two sites.

### C.2.3 Energy Expenditure, Body Composition and Markers of Chronic Disease

Our international collaborative study on hypertension has led to new insights on the relationship between EE, body composition and markers of chronic disease. In our initial survey, we noted a robust correlation between resting EE and BP. This observation was subsequently confirmed in a total sample of 1,567 individuals from independent samples in Nigeria, Jamaica and the US [121]. Resting EE is in turn strongly correlated with weight and BMI, since adiposity leads to an obligatory increase in muscle mass required for movement. Multivariate analysis subsequently confirmed, however, that the impact of resting EE on BP is independent of BMI and weight. In fact, no measures of adiposity remain significant after accounting for resting EE [121]. This observation suggests that at least one important mechanism by which obesity leads to increases in BP is through the correlated increase in muscle mass and resting EE. To further test this hypothesis, we recently completed a person-level meta-analysis of body composition and BP in 18,072 individuals from the populations we propose to include in this study [137]. Persons at the upper end of the BMI distribution have higher percent body fat, thus a unit increase in BMI leads to a smaller increase in lean mass than a comparable increase in BMI among the lean. Under the assumption that it is the increase in lean mass that influences BP, the slope of the BMI-BP relationship should be steeper among the lean. In meta-regression analysis of 13 population samples, we, in fact, observed a strong negative relationship between mean BMI and slope of the BMI-BP correlation for both SBP and DBP ( $p < 0.001$ ). This relationship had never been detected in studies of individual populations and demonstrates the value of studies that sample from a broad range of social contexts. Using this international comparative design, we have also detected novel

relationships between BMI and physiologic variables (e.g., leptin and angiotensinogen) as well as impacts of environmental factors on the heritability of common traits (e.g., height, BP, and BMI) [137]. We have also reported on the relationship between PA, measured using DLW, and blood pressure; in a small sample of Nigerian, Jamaican, and African-American adults, activity EE, independent of body size or composition, was found to be inversely associated with both SBP and DBP [48].

The Loyola-Ibadan's Women's Study allowed us to examine the relationship between components of the energy budget and hormones and cytokines associated with obesity and glucose homeostasis. Along with measurements of total, resting and activity EE, fasting blood samples were obtained from the women in both

rural Nigeria and suburban Maywood. Among the significant associations recorded was an inverse association between activity EE and fasting insulin after controlling for body size and composition among the Maywood women ( $r=-0.24$ ,  $p<0.05$ ), but none among the Nigerian women. This lack of association among the Nigerian women is likely due to the relatively modest variability in insulin levels compared to the Maywood cohort ( $10\pm6$  vs  $24\pm19$   $\mu$ U/mL). As can be observed in Figure 5, the distribution of insulin concentrations is much narrower among the Nigerian than the US women. These data illustrate the obvious importance of AEE in maintenance

of glucose homeostasis. Interestingly, in regression models resting EE was a significant determinant of both leptin ( $p<0.005$ ) and adiponectin ( $p<0.05$ ) concentrations in both cohorts of women after controlling for body composition and age. In addition, resting EE was inversely associated with ghrelin in the Nigerian cohort ( $p<0.01$ ). These observations require confirmation. It has been hypothesized that high adiponectin may be protective of the increased risk of obesity that theoretically accompanies low resting EE [106], however, our group demonstrated recently that there was no association between low resting EE and subsequent weight gain[138]. This preliminary data does suggest a strong link between hormones and the energy budget and deserve further investigation in larger samples.

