#### *D.7.1.1.2 AEE, Adipocytokines and Diabetes*

We will have measures of fasting glucose and insulin, adiponectin, ghrelin and leptin on this unique sample of 5 populations of African origin. The following additional variables will be collected: age, gender, place of birth, prior medical history, occupation, education, height, weight, activity by questionnaire, pregnancy history, and season of exam.

In the analysis phase we will first compare the descriptive characteristics in each population (e.g., mean adipocytokine/hormone values and prevalence of hyperglycemia). We will explore the univariate correlation structure for the continuous variables listed above. We will then construct multivariable regression models to assess the potential independent role of AEE as a predictor of risk factor status independent of body composition. Risk factor status will be examined as continuous and categorical outcomes. For instance, how is insulin level affected by AEE after accounting for body composition?

An important focus of these analyses will be looking for potential heterogeneity of risk relationships across sites. Three main aspects are of interest, namely whether the AEE-risk factor (e.g. insulin level) relationship is present, or of the same magnitude, in each sample and whether there exists co-variation with the mean level of AEE; testing for interaction will be undertaken where appropriate. Precisely,

*Relative effect of AEE on risk factor:* We will examine the magnitude of the association using 1) regression coefficients; 2) standardized regression coefficients. This approach allows within and between site comparisons. It is recognized that cross-site comparisons could be problematic when using standardized regression coefficients since the standard deviation of the variables involved may differ across sites. In this case, standardized regression coefficients will be obtained using pooled estimates of the mean and standard deviation.

*Co-variation of the association with mean level of AEE:* Multilevel models will be applied, in which the site specific variable, mean AEE, will be used to estimate the effect of the average AEE on the regression coefficient.

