## D.7.2 Power Analysis

A statistical justification for the selected sample size is provided for each aim of the study according to the suggested analytical plan. Sample size estimation for each of these hypotheses will be obtained, and the maximum number required to test them with sufficient power (80% or higher) will be selected.

- 1) PA is negatively related to percent body fat and CV risk factors in the study populations at baseline.

It has been previously estimated (cf. Preliminary Studies) that the correlation between PA, measured with DLW, and body composition is between -0.6 and -0.5. A correlation of -0.33 or smaller (larger in absolute value) will be detectable with 83% power and maximum probability of type I error alpha = 5% using a one-sided Fisher's Z test and 75 subjects per site [194].

- 2) PA is negatively related to change in body fat composition.

- a) *Physical Activity Measured by Accelerometer:*

PA, measured by the accelerometer, is associated with changes in body composition. For design purposes we will use the approach described above in the analysis section (see D.7.1.2. method 3). That is, two AEE groups will be formed by using the median AEE as the cut point. A method developed by Frison and Pocock [195] will be applied to compare mean changes between groups in a longitudinal analysis, adjusting for baseline values. In this method the following assumptions are made: the correlation between any 2 weight determinations is ~ 0.60 and the minimum acceptable difference between the means is 0.25 standard deviations (i.e., effect size equals 0.25) [186]. There will be one baseline measure of weight and two follow-up measurements. An analysis of covariance approach will be used to adjust for baseline values. Thus, to detect the pre-specified minimum difference with 90% statistical power we will need to accrue 460 subjects per AEE group (230 in the Low and 230 in the High group). We will accrue a total of 500 individuals per site in anticipation of a conservative total attrition rate of ~ 20%.

- b) *Physical Activity Measured by Doubly Labeled Water:*

The correlation between AEE and change in body composition is anticipated to be weaker (i.e., smaller in absolute value) than that observed between AEE and body composition at baseline. Data from previous studies (cf. Section C: Preliminary Studies) suggest that the association between AEE and body composition remains constant across studies.

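### The D.7.2 item 1 power statement covers CV risk factors but is justified only for body fat; at the one numeric DLW pilot correlation with a risk factor (-0.24), 75 per site give about 67% one-sided or 55% two-sided power

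*Combined protocol and SAP*

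**What the plan says.** D.7.2 sets a target for every hypothesis: "the maximum number required to test them with sufficient power (80% or higher) will be selected". Its first item reads "PA is negatively related to percent body fat and CV risk factors in the study populations at baseline". The justification is a previously estimated correlation between DLW-measured activity and body composition: "body composition is between -0.6 and -0.5". The power claim follows: "A correlation of -0.33 or smaller (larger in absolute value) will be detectable with 83% power", at "maximum probability of type I error alpha = 5" percent, "using a one-sided Fisher's Z test and 75 subjects per site". Item 1 gives no assumed correlation for any CV risk factor.

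Section A, Specific Aim 5, lists insulin among the biochemical risk factors for cardiovascular disease. C.2.3 reports what the Loyola-Ibadan Women's Study found for insulin, with energy expenditure measured by DLW (C.2.2.2): an "inverse association between activity EE and fasting insulin after controlling for body size and composition among the Maywood women", r = -0.24, p < 0.05, and no association in the Nigerian women. C.2.3 also mentions an inverse relation of DLW-measured activity energy expenditure (AEE) with systolic and diastolic pressure in a small sample, but gives no coefficient.

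D.7.1.1.2 takes up the same adjusted question, with insulin as its example. One of its stated interests is "whether the AEE-risk factor (e.g. insulin level) relationship is present, or of the same magnitude, in each sample".

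**The concern.** A detectable-effect statement supports a sample size only if effects of that size are plausible for the outcome it covers. For percent body fat, item 1 supplies that plausibility: -0.5 to -0.6 is well beyond -0.33. For CV risk factors it supplies nothing, and the one number elsewhere in the plan is weaker than -0.33. A reader of item 1 would take it that the 75-person DLW subset at each site meets the 80% target for risk factors too. If the true correlation is near the pilot value, it does not, and a null DLW result for a risk factor at one site would carry less information than item 1 suggests.

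The wording matters more because D.7.1 announces a power calculation for four primary hypotheses, the fourth concerning hormones and insulin sensitivity, while D.7.2 has items for only three. The mention of CV risk factors in item 1 is the only power wording that reaches insulin.

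**Working it through.** **Inputs.** From D.7.2 item 1: r = -0.33, n = 75 per site, alpha 5%, one-sided Fisher's Z, stated power 83%. From C.2.3: r = -0.24. From D.7.1.1.1: 500 accelerometer participants per site and 375 DLW participants in total. From B.5: accelerometer-DLW correlation 0.62 for kcal/day.

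**Formula.** Power = Φ(atanh|r| × √(n − 3) − z), with z = 1.645 one-sided or 1.960 two-sided.

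**The plan's own figure.** atanh(0.33) = 0.3428 and √72 = 8.485, so the product is 2.909.
- One-sided, as stated: Φ(2.909 − 1.645) = 89.7%.
- Two-sided: Φ(2.909 − 1.960) = 82.9%.

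Simulation with 100,000 replicates gives 90.2% and 83.6%. With all 75 participants, the stated 83% is therefore the two-sided figure. One-sided with 60 participants (a 20% loss) would give 82.7%, but the plan applies no loss to the baseline analysis.

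**At the pilot correlation.** atanh(0.24) = 0.2448, and 0.2448 × 8.485 = 2.077.
- One-sided: Φ(2.077 − 1.645) = 66.7% (simulation 67.0%).
- Two-sided: Φ(2.077 − 1.960) = 54.7% (simulation 55.0%).
- Treated as a partial correlation with one to three covariates: 65–66% one-sided, 53–54% two-sided.

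Like for like, moving from -0.33 to -0.24 takes power from 90% to 67% one-sided, or from 83% to 55% two-sided.

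**Smallest |r| with 80% power at n = 75.**
- One-sided: tanh((1.645 + 0.842)/8.485) = 0.285.
- Two-sided: tanh((1.960 + 0.842)/8.485) = 0.32.

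Both are stronger than 0.24.

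**Precision of the pilot value.** C.2.3 gives no n for the insulin analysis. If all 180 US women in Table 3 contributed (an assumption), the 95% interval on the Z scale is 0.2448 ± 1.96/√177, that is 0.097 to 0.392, or r from -0.10 to -0.37.

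**Other analyses of the same question.**
- Pooled DLW, n = 375, r = -0.24 common to all sites: 0.2448 × √372 = 4.72; Φ(4.72 − 1.96) = 99.7% two-sided. Four site terms barely change this.
- Accelerometer, 500 per site, with r attenuated by 0.62 (an assumption, since 0.62 is not specific to AEE): r = -0.24 × 0.62 = -0.149; atanh = 0.150; 0.150 × √497 = 3.34; Φ(3.34 − 1.96) = 91.7% two-sided, 95.5% one-sided. With assumed attenuation of 0.6 or 0.5, two-sided power is 90% or 77%.

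**The case against.** The strongest reply is that item 1 is conditional: it states the power if the correlation is -0.33 or stronger. A reader might infer that the plan asserts this value for CV risk factors, but it does not, and lower power at a weaker correlation contradicts nothing. That stands. What remains is that one heading extends the statement to outcomes for which item 1 offers no effect size.

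Second, CV risk factors appear in this hypothesis only in D.7.2. Section A, D.1.2 and D.7.1 word it for percent body fat alone, and Section A calls the adipocytokine and ghrelin work exploratory. This also stands; it makes the point one about the scope of a power statement, not about a primary test.

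Third, -0.24 is a single adjusted estimate from women at one site, and its approximate interval includes -0.33. It cannot represent every risk factor, and the blood pressure finding has no coefficient to set beside it. That stands too, though the absence of an association in Nigerian women points toward weaker effects, not stronger ones.

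Fourth, D.7.1.1.2 does not tie the risk-factor analysis to DLW, and D.7.1.1.1 plans a similar structure for both exposure measures. The larger accelerometer sample is therefore already available for this question.

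A reader might also infer that, because D.7.1.1.2 asks about presence in each sample, a miss at one site would be taken as site heterogeneity, and might multiply per-site power across five sites. The documents do not support this. No decision rule requires significance at every site. D.7.1.1.2 compares regression coefficients and uses multilevel models, and it calls the AEE-by-site interaction results exploratory for lack of power. D.7.2 says the study is not powered for differences in association across sites.

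**Conclusion.** The point holds as a limit on the per-site DLW analysis of CV risk factors. At r = -0.24, that analysis has about 67% power one-sided or 55% two-sided, against a target of 80%. These figures assume that the pilot correlation is a fair planning value for a risk factor at a given site and that all 75 DLW participants are analysed.

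A reader might conclude that the study as a whole is underpowered for risk factors. The documents do not support that. The pooled DLW analysis exceeds 99% if the association is common to all sites. The accelerometer analysis has about 92% two-sided power per site if 0.62 is the right attenuation, though 77% if it is 0.5. The power statement for percent body fat is not in question except for its sidedness: with 75 participants, 83% is two-sided, and the named one-sided test gives about 90%.

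**What to change.** In D.7.2 item 1:

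1. Restrict the -0.33 statement to percent body fat and correct the sidedness: either two-sided with 83%, or one-sided with about 90%.
2. For CV risk factors, state that the per-site DLW analysis has about 67% (one-sided) or 55% (two-sided) power at the pilot r = -0.24, and that this estimate is adjusted, from women at one site, and imprecise.
3. Name the main tests for CV risk factors, each with its own power and assumption: the 500-per-site accelerometer analysis (about 92% two-sided under attenuation of 0.62) and the pooled DLW model with site terms (n = 375, over 99% if the association is common to all sites).

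This costs a few sentences. It needs no additional participants, measurements or analyses; one stated figure becomes less favourable.
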